# 6.7 Recruitment

It is recommended that during the development of this research protocol, the principal investigator requests the approval of the Research Ethics Committee and the Research Committee, as well as the authorization to the relevant regulatory entity, to publish or disseminate in the mass media, the invitation to participate in the study to those people who meet the eligibility criteria.

It is possible to discuss with other health professionals the opportunity for healthy subjects to be evaluated by an ophthalmologist at no cost, as well as cabinet exams that will allow the more accurate determination of their ocular clinical status by participating in a sponsored clinical research protocol. by Sophia Laboratories, SA of C.V.

# 7. Methods Assignment of the intervention

# 7.1 Generation of the allocation sequence

The random numbers will be generated using the online tool

#### : www.randomization.com

3 strata corresponding to the intervention groups will be used, which will be balanced for a research center. The allocation will be 1: 1: 1.

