# 6.1.1 Organization of the center

Each study center will have a principal investigator (PI). The PI is the ophthalmology specialist in the clinical study.

The PI is responsible for forming a multidisciplinary research team to carry out the clinical study according to protocol, under its scientific guidance. It is the prerogative of the IP the design of the organization of its center and the selection of the personnel that will perform the functions. Nevertheless, the minimum organization of the research team requested by the sponsor requires the figure of sub-researcher, study coordinator and pharmacist. (See **Figure 1**)

Any person to whom the PI designates, under his / her responsibility, a part of the follow-up of the study (co-investigator, under-researcher, nurse, etc.) or a specific function of participation in the study (pharmacist, administrative assistant, study coordinator, etc.) should appear in the "Delegation of Responsibilities" format.

Figure 1 Minimum organization of the center

The "Delegation of Responsibilities" and the "Organizational Chart of the Center" must be delivered to the sponsor before the start of the study and updated if the members or their responsibilities are changed.

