# 6.5.2 Diagram of the study.

An enrollment time of 30 days is estimated for the total sample.

In order to increase the safety of the participants with the use of the products under investigation, a partial analysis will be carried out following a modification to the Fibonacci method. Said methodology will consist of including 33% of the total sample size (3 subjects per group, n = 9), which will complete all the visits and procedures described. Once this group of 9 subjects has finished their participation in the clinical study, they will proceed to perform a blinded analysis. During the period in which this sub-analysis is carried out, the inclusion of new participants will be restricted. Inclusion will resume when the sponsor notifies each research center.

In addition to safety, the therapeutic adherence will be evaluated and problems related to the procedures will be solved, should they arise.

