# 8.3 Statistical methodology

#### 8.3.1 Analysis of primary and secondary outcome variables.

The statistical analysis will be carried out by personnel from Sophia Laboratories, S.A. of C.V The statistical program SPSS version 19 (IBM Corporation, Armonk, NY, USA) will be used.

The designated personnel will be blinded to the intervention groups. The coding will be done using consecutive numbers for each intervention group.

The data will be collected and sorted in an excel sheet. Later they will be exported to the platform of the SPSS program. The variables will be categorized according to their nature.

CONFIDENTIAL

The result of the continuous quantitative variables will be presented in measures of central tendency: media, standard deviation and ranges. **See Table 5**. Scales to be used

The normal distribution of the results will be obtained by the Kolmogorov-Smirnov test.

The statistical analysis of the continuous **quantitative variables** to find significant differences (p) will be the following:

- Intra-group analysis: Wilcoxon rank test.
- Inter-group analysis: Kruskal-Wallis test.

The level of difference to consider significance will be an alpha of 0.05 or less.

The result of nominal and ordinal qualitative variables will be presented in frequencies, proportions and percentages. See table 1 (section 6.4.3).

The statistical analysis to identify significant differences of the **qualitative variables** will be done by creating 2x2 contingency tables and will be done as follows:

- • Intra-group difference: McNemar test.
- • Difference between groups: χ2 test (Chi-square) of Pearson.
- The level of difference to consider significance will be of an alpha of 0.05 or less.
- For the reporting of adverse events all eyes of those participants who were randomly assigned to an intervention group after the baseline visit will be considered. The results will be expressed in number of cases (eyes).
- The final report of the results will be shown in tables or graphs, as appropriate.
- It will be considered that the investigational drug is safe and tolerable when there are no clinical and statistical differences in all the variables of primary outcome, with respect to its comparators.

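### The between-arm tests ignore center and stage, two factors the design balances; this costs power once the subject is the unit of analysis, and should be fixed together with the eye-level unit.

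*Combined protocol and SAP*

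**What the plan says.** Section 7.1 describes three arms "which will be balanced for a research center. The allocation will be 1: 1: 1". Stage is not mentioned there. It comes from section 6.5.2, where the first step is "including 33% of the total sample size (3 subjects per group, n = 9"). Enrollment then stops for the interim look: "During the period in which this sub-analysis is carried out, the inclusion of new participants will be restricted". Besides safety, adherence is reviewed and "problems related to the procedures will be solved, should they arise". Then, "Inclusion will resume when the sponsor notifies each research center".

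The number of centers is never stated. Section 6.1.1 ("Each study center will have a principal investigator (PI")) and the restart rule in 6.5.2 allow for several, while sections 7.1 and 7.3 speak of one.

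In section 8.3.1 the tests between arms are "Inter-group analysis: Kruskal-Wallis test" for quantitative variables and "Difference between groups: χ2 test (Chi-square) of Pearson" for qualitative ones, each at 0.05. Neither has a center or stage term. The same section calls the product safe and tolerable when the primary variables show no clinical and statistical differences from the comparators. Section 6.6.1 has both eyes contributing, for 60 eyes in all, and no method is given for the correlation between a subject's two eyes.

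**The concern.** When arms are balanced within a factor that affects the outcome, that factor cannot bias the arm comparison. A test that ignores it still leaves its variation in the error term. The rejection rate under no difference then drops below the nominal 5%, and power drops with it.

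Several primary variables could plausibly shift with site or stage. Each center uses its own slit lamp and lighting technique (6.4.3.4), hyperemia and staining are graded by an observer, symptoms are obtained by direct questioning (6.4.3.9), and procedures may be corrected after the first 9 subjects. In most trials lost power works against the sponsor. Here a non-significant result supports the safety conclusion, so lost power works in favor of it.

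**Working it through.** **Inputs from the protocol.** 24 × 1.25 = 30 subjects, 10 per arm. Stage 1 has 3 × 3 = 9 subjects, leaving 30 − 9 = 21 (7 per arm) for stage 2. (9/30 is 30%, not the printed 33%; nothing turns on this.) Alpha is 0.05. The plan states no figure for center or stage effects.

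**Assumptions, not in the protocol.** One to five centers; center share of variance 0 to 0.5; stage shift 0 to 1 SD; between-eye correlation 0.5 to 0.9; one arm shifted by 1 or 1.2 SD.

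**Tests.** Kruskal-Wallis: H = 12/[N(N+1)] · Σ(R_j²/n_j) − 3(N+1), referred to chi-square on 2 df. Aligned-rank: subtract the center and stage effects, rank the residuals, and test arm by F with the factors in the model.

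**Step 1. Hand check, one center, subject means.** With correlation 0.7 the mean of two eyes has variance (1 + 0.7)/2 = 0.85. A stage shift of d SD, balanced over arms, adds d² × (9/30) × (21/30) = 0.21d² to the apparent error. Under no difference, H shrinks by about the ratio of true to apparent error, and on 2 df the tail area is exp(−x/2), with critical value 5.991.

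- d = 0.5: 0.85/(0.85 + 0.0525) = 0.942; exp(−2.996/0.942) = 0.042. Simulated: 0.039.
- d = 1: 0.85/(0.85 + 0.21) = 0.802; exp(−2.996/0.802) = 0.024. Simulated: 0.022.

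**Step 2. Simulation at subject level** (40,000 runs per setting, correlation 0.7, power for a 1.2 SD harm). KW is unadjusted Kruskal-Wallis.

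| Centers | Center share | Stage shift | KW type I | Adjusted type I | KW power | Adjusted power |
|---|---|---|---|---|---|---|
| 3 | 0 | 0 | 0.045 | 0.053 | 0.782 | 0.797 |
| 3 | 0.1 | 0.5 SD | 0.029 | 0.052 | 0.768 | 0.842 |
| 3 | 0.3 | 0.5 SD | 0.018 | 0.052 | 0.784 | 0.921 |
| 3 | 0.5 | 1 SD | 0.004 | 0.055 | 0.718 | 0.980 |
| 1 | – | 0.5 SD | 0.039 | 0.051 | 0.751 | 0.802 |
| 1 | – | 1 SD | 0.022 | 0.053 | 0.672 | 0.803 |

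The small gap in the first row reflects the slightly different sizes of the two tests, not a real gain. The adjusted test here aligned on center-by-stage cells filled in complete blocks of three, which is a favorable case.

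An additive adjustment (center plus stage) was simulated separately for a 1 SD shift. Type I error stayed at 4–6%. With two centers and no effects, power was 63% unadjusted and 65% adjusted. With one to five centers, center share 0 to 0.3 and stage shift 0.3 to 0.5 SD, the gain was about 4 to 23 points.

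**Step 3. The tests as planned, on 60 eyes.** Treating two eyes with correlation r as independent multiplies H by about 1 + r. With no center or stage effect the type I error is about exp(−2.996/(1 + r)):

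- r = 0.5: 0.136 (simulated 0.133)
- r = 0.7: 0.172 (simulated 0.172)
- r = 0.9: 0.207 (simulated 0.212)

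At r = 0.7 and three centers, center and stage effects lower this to 0.137 (share 0.1, 0.5 SD) and 0.100 (0.3, 0.5 SD). It falls below 0.05 only in the extreme setting (0.5, 1 SD: 0.038). Adjusting for center and stage while still counting eyes removes that offset and brings the rate to 18–20%.

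**Step 4. Binary variables.** With a common 8% event rate at subject level, Pearson chi-square has type I error 0.028. With stage rates of 20% and 2.86% (mean (3 × 0.20 + 7 × 0.0286)/10 = 0.08) it is 0.019. Power for a 30-point excess in one arm is 0.428 with equal stage rates and 0.416 with unequal ones. The effect on binary outcomes is therefore small in this example. Cochran-Mantel-Haenszel itself was not simulated.

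**The case against.** A reader might infer that the planned tests are conservative. They are not: on 60 eyes the false-positive rate exceeds 5% in nearly every setting tried (step 3). The narrower point survives. The eye comfort index and the laboratory tests are recorded once per subject, so eye clustering does not arise there. For the other variables, two errors that partly cancel do not make a valid test, and the power loss is what remains once the eye unit is corrected.

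A reader might also infer that full stratification is a safe remedy. With 9 subjects in stage 1, center-by-stage strata are tiny; with five centers they average 9/5 = 1.8 subjects for three arms. A joint van Elteren test, with stage 1 spread at random over centers, had power of 48% against 54% for Kruskal-Wallis with two centers and no effects, and 37% against 54% with five. That objection stands, and it is why the adjustment should be additive.

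Three further objections limit the size of the point:

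- The number of centers and both effects are assumed, and the correction of procedures is conditional on problems arising.
- Section 5.5.2 mostly speaks of changes. If change from baseline is compared, stable center and stage offsets largely cancel. Section 8.3.1 does not say that it is.
- Cytology samples are sent out for histopathological analysis and blood goes to a laboratory designated by the sponsor, so those readings depend less on site; the cytology sampling itself does not.

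**Conclusion.** The concern holds in a limited, conditional form. The design balances center and stage and the between-arm tests use neither. At subject level this makes Kruskal-Wallis conservative whenever either factor affects the outcome: type I error about 0.018 to 0.039 for stage shifts of 0.5 SD and center shares up to 0.3. Under the assumptions in step 2, additive adjustment gains roughly 4 to 23 points of power for a 1 SD shift, and about nothing when there are no effects. With one center only stage matters, and in the one-center settings of step 2 (1.2 SD harm) the gain is 0.802 − 0.751, about 5 points, at a 0.5 SD stage shift.

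The protocol does not support saying that the tests it specifies, on 60 eyes, are conservative or for that reason biased toward a finding of safety. The eye-level unit is the larger problem and acts in the opposite direction. This is a minor refinement, and it does not bear on the sample size.

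**What to change.** Make one change to section 8.3.1 with two parts that go in together:

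1. Use the subject as the unit (mean of both eyes for quantitative variables), or use a method that accounts for paired eyes.
2. Adjust between-arm tests for stage (first 9 against last 21), and for center if more than one opens, as additive factors: an aligned-rank test for quantitative and ordinal variables, and Cochran-Mantel-Haenszel stratified by one factor for binary ones.

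Do not stratify by center and stage jointly, because the cells are too small. Do not add the factors while eyes are still counted as independent, because that raises the false-positive rate. The same edit should say whether final values or changes from baseline are compared. The cost is SAP wording and a few degrees of freedom: one for stage and one for each center beyond the first.

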# 7.2 Blinding mechanism

Blinding will be performed by personnel assigned by the Clinical Operations Management of Sophia Laboratories, S.A de C.V. This will consist of the elimination of the primary label (commercial) in the case of Xyel Ofteno® and Systane Ultra® and the placement of a label identical to the other interventions. Because the bottle in which Systane Ultra® is packaged differs in the color and shape of the lid used by Xyel Ofteno® and PRO-087, a masking will be carried out on the primary packaging which will be identical for the three interventions.

# 7.3 Implementation

The allocation sequence will be generated by personnel assigned by the Clinical Operations Management of Sophia Laboratories, S.A. of C.V.The research center will receive a set of envelopes which will contain the intervention number individually. The envelopes will be identical on the

Sophia Laboratories, S.A. of C.V.

outside. Each of these envelopes will be shown to the participants for their election by the principal investigator or by a designated member of their team.

# 7.4 Blinding (Masking)

The blinding will correspond to the research subject and the principal investigator. In addition, the statistical analysis will be carried out in a blinded manner for the partial and final analysis.

The masking will be done using boxes in the identical primary packaging in the three groups. Blinding for the research subject and the researcher will be done by replacing the commercial labels in the case of the comparator in the bottles and the use of identical labels that contain the assignment number.

# 7.4.1 Opening of blinding.

Blinding may be opened in the following cases:

- 1. Presence of a serious adverse event.
- 2. Safety alarm due to the use of the drugs under study.

3. In case the sponsor determines it for any security reason or other reason that it considers pertinent

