# 9.2 Preliminary analysis and early termination of the study

The partial analysis described in section 6.5 and 8.3.2 will allow the sponsor to make a decision about the early termination of the study in the event that the safety of the participants is compromised.

The early termination of the study will be considered in the following cases:

- 1. Presence of serious adverse events in more than 5% of the participants in each intervention group.
- 2. The competent authority (COFEPRIS) considers it for security alerts.
- 3. The Sponsor determined it for his convenience or eventualities such as: economic support, manufacturing errors, etc.
- 4. Lack of recruitment as expected.

In case the decision is the early termination of the clinical study, all the research centers will be informed within the first 24 hours by the available communication channels. Likewise, the corresponding authority in each country will be informed (if applicable) and the Ethics Committees involved.

Each research center has the obligation to inform the subjects that participate in the clinical study in a period no longer than 24 hours, after receiving the information from the sponsor. You must inform all the subjects involved in any phase of the study.

The result of the preliminary evaluation will be in charge of the Clinical Operations Management and the Medical Management of Sophia Laboratories, S.A. of C.V., which will have the faculty to determine the fate of the present protocol, as they deem convenient.

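### Section 7.4.1 lets the sponsor open the blind for a non-safety reason before database freeze, so the promised blinded analyses are not secured

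*Combined protocol and SAP*

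**What the plan says.** - **Opening the blind.** Section 7.4.1 lists a serious adverse event, a safety alarm about the study drugs, and a third ground: "In case the sponsor determines it for any security reason or other reason that it considers pertinent".
- **Promise of blinding.** Section 7.4 blinds the subject and the principal investigator, and adds that "the statistical analysis will be carried out in a blinded manner for the partial and final analysis". On the first 9 subjects (3 per group), section 6.5.2 says: "they will proceed to perform a blinded analysis". Section 8.3.1 says of the analysts: "The statistical analysis will be carried out by personnel from Sophia Laboratories" and "The designated personnel will be blinded to the intervention groups". Each group is represented by a consecutive number.
- **Sequence and masking.** Section 7.3: "The allocation sequence will be generated by personnel assigned by the Clinical Operations Management of Sophia Laboratories". Section 7.2: "Blinding will be performed by personnel assigned by the Clinical Operations Management of Sophia Laboratories".
- **Preliminary decision.** Section 9.2: "The result of the preliminary evaluation will be in charge of the Clinical Operations Management and the Medical Management of Sophia Laboratories". The same paragraph gives them the power to decide what becomes of the protocol.
- **Freeze.** Section 8.2 leaves the last review and the standard for freezing the database to the sponsor's Scientific Committee. It does not mention the blind.

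**The concern.** A blinded analysis protects against bias only if arm identity stays unavailable until the data and the exclusions are fixed. Items 1 and 2 of section 7.4.1 are ordinary safety grounds and are not in question. The second half of item 3 is different in kind: it is a standing permission for the sponsor to open the code whenever it sees cause.

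Two uses of the data depend on the blind. The first is the decision to continue or stop after the partial analysis. The second is the final conclusion in section 8.3.1, which rests on there being no clinical and statistical differences from the comparators in any primary variable. No margin is given for a clinical difference, so that part is a judgement. The sponsor makes PRO-087 and also Xyel Ofteno, one of the two comparators, so knowledge of the arms would not be neutral for it.

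**Working it through.** The plan gives no figure to reproduce. The check is a reading of the sections against each other.

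1. **Scope of item 3.** The translation uses security where safety is meant (for example the security outcome variables in section 6.4.1). Item 3 sets other reasons beside security reasons, so its second half covers non-safety reasons.
2. **Timing and authority.** Section 7.4.1 sets no time limit. It does not say who authorises opening, whether it covers one subject or all, or how it is recorded. Section 8.2 deals with the freeze without reference to the code. Section 8.3.1 blinds the analysts without saying until when. Section 9.3.1.1 appears to foresee opening in order to attribute an adverse event, which is a safety purpose, and adds no rule on timing.
3. **Against the promise.** Sections 6.5.2, 7.4 and 8.3.1 say that the analyses are blinded. Section 7.4.1 permits the sponsor to end that state at any point before them. Both can be followed to the letter, so the promise holds only as long as the sponsor chooses not to use item 3.
4. **Separation of roles.** Sections 7.2, 7.3 and 9.2 name the same Clinical Operations Management. In the first two it assigns the staff who mask the products and generate the sequence; in the third it shares charge of the preliminary result with Medical Management. No sentence says who holds the code or keeps its holders apart from the decision.
5. **Reach of a single opening.** The analysis uses one number per group. Anyone who learns one subject's allocation, and can link that subject to a group number, knows the identity of that whole group.
6. **What a fix must leave intact.** Section 9.2 states its serious-adverse-event criterion by intervention group, at more than 5%. One event is 1/3 = 33% of a group at the partial analysis and 1/10 = 10% at full size, so it puts that group above 5%. The wording may require every group to exceed the threshold. Either way the criterion is read by group, and item 2 of section 7.4.1 concerns the study drugs. A rule that allowed opening for single subjects only would collide with both.

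**The case against.** The strongest reply is that the plan does protect the people it says it protects. Section 7.4 claims blinding for the subject, the principal investigator and the statistical analysis, not for the whole sponsor, and section 8.3.1 blinds the analysts with coded groups. This stands, and it rules out several stronger readings.

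- A reader might infer that the sponsor or its analysts are in fact unblinded. The text does not say so.
- A reader might infer that those who judge the preliminary result hold the code. Sections 7.2 and 7.3 refer to personnel assigned by Clinical Operations Management; a shared department does not make them the same people. Sections 9.3.1 and 10.9.1 place a Scientific Committee within Clinical Operations, but that does not show that it knows the arms.
- A reader might infer that queries and exclusions can be steered by arm. Adherence and visit exclusions follow fixed rules: below 50% in section 6.2.3, above 60% in section 8.3.1, and Visits 1 and 2 completed in section 8.3.3. Section 8.2 has the investigator's team make corrections to the case report form.
- A reader might put a number on the harm, since one subject of 10 is 10 percentage points of an arm. No section gives the sponsor power to reclassify a subject, so that figure does not measure this defect.

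Section 4, on administrative structure, was not in the text available, and a separation of roles may be set out there. That could answer the point about roles. It would not change what item 3 permits.

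It is also fair to say that this is a small exploratory phase I study with mainly descriptive objectives, where such roles are often kept in house. That lowers the stakes. It does not remove the point, because the safety conclusion in section 8.3.1 rests on between-group comparison.

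**Conclusion.** The point holds in a limited form. Item 3 of section 7.4.1 is a stated rule that allows opening for non-safety reasons with no link to the freeze, and this leaves the promised blinded analyses unsecured. The overlap at Clinical Operations Management adds weight because no separation is stated, but it is not evidence of a breach.

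There is no numerical size: sample size, power and significance level are untouched. What is exposed is the decision after 9 of 30 subjects and the blinded status of the partial and final analyses. The conclusion assumes that security means safety in item 3, and that no part of the protocol outside the available text ties the code to the freeze.

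**What to change.** - In section 7.4.1, end item 3 after its safety part and delete the wording that admits any other reason.
- State that, before the documented database freeze, the code may be opened only on the safety grounds already in section 7.4.1: items 1 and 2 and the safety part of item 3. Each opening gets a dated record of who opened it, why, and for which subjects.
- State that the code is otherwise released only after the freeze and after exclusions are fixed.
- State that, apart from a recorded safety opening, the staff who generate and hold the sequence take no part in the preliminary evaluation, the freeze or the analysis.
- Keep the existing safety-alarm route, including at product level, and reconcile its wording with the group-level criterion in section 9.2.

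The cost is a few sentences and an assignment of custody within the sponsor. Whether the sponsor can make that assignment without extra staff is not shown in the documents. The downside is that the sponsor loses the option of opening the blind early for non-safety reasons.
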